4.5.1 Overview of Randomization and Intervention Conditions (Aim 1)

Couples will be randomized with an allocation ratio of 2:1 to either the IE or the Educational Control (Living Healthy Together) condition, in order to maximize data generated on the active condition, with stratification by age at diagnosis (≤ 45 vs. > 45) using the age obtained by patients during the screening. Because of the broad intimacy targets of this intervention, outcomes may not differ by menopausal status and therefore we will not stratify by this variable. However, because sexual function can differ by menopausal status, we will investigate menopausal status as a possible moderator of outcome in the intervention group for future research.

Randomization will occur once both members of the couple have consented, completed baseline surveys, and are scheduled for their first intervention session. At this time, the couple will be sent sealed study materials along with the instructions to leave the envelopes sealed until they “meet” with their interventionist for session 1. It is important to keep the study condition a secret from participants until Session 1 to reduce the chances for unequal drop-out prior to Session 1, which could occur if patients/partners are more motivated to attend sessions in one study group as opposed to the other.

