13.1.1. Primary and Secondary Outcome Variables

13.1.1.1. Primary outcomes are feasibility and acceptability of the study. Feasibility will be measured through study accrual, attrition, and session completion. Acceptability is measured using the CSQ-8 (See Self-report Materials in Appendix).

13.1.1.2. Secondary outcomes are preliminary efficacy of the study in patient and partner sexual outcomes (sexual function, sexual satisfaction and intimacy, sexual distress), patient and partner relationship outcomes (emotional intimacy, sexual communication, relationship quality), and patient psychosocial outcomes (body image distress, psychological distress). The measures assessing these outcomes can be found in Table 3 above.

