13.1.2. Analyses

13.1.2.1. Feasibility. Analyses will be descriptive. We aim for accrual at a rate of 30% to match our prior study,⁴² but a rate over 20% will be acceptable. Attrition at levels greater than those found by similar studies⁴⁷ (e.g., 30%) will be considered unfeasible. 80% of participants completing the 4 sessions is considered adequate.

13.1.2.2. Acceptability. Analyses will be descriptive. Adequate acceptability of the study will be indicated by a group median score ≥ 28 on the CSQ-8,⁷⁶ representing a fairly high score across a range of studies, including a behavioral marital therapy randomized controlled trial.⁷⁷

13.1.2.3. Preliminary efficacy. Preliminary efficacy of the IE intervention on patient and partner sexual outcomes, patient and partner relationship outcomes, and patient psychosocial outcomes will be established using an effect size calculation method that is appropriate for small sample sizes³⁴ that our team has employed previously.^{34,49} First, pre-post changes scores are calculated for each participant. Second, the between-group effect size is calculated by subtracting the mean control group change score from the mean IE group change score. This difference is then divided by the standard deviation of the pooled change score. Given that multilevel dyadic analyses are questionable in small sample sizes,⁷⁸ we will consider dyadic analyses, including actor-partner effects,⁷⁹ in the planned R01.

Because our primary goal through the analyses for this aim is to generate effect sizes for a larger planned study, we will conduct the analyses described above using data from study completers. However, we will also attempt to obtain post-treatment surveys even for couples who have dropped out of the study during the intervention phase, to allow us to conduct intent-to-treat analyses. Patients without any post-treatment data will have baseline data used in these analyses.

13.2. Statistical Analyses for Aim 2

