13.2.4. Sample Size Calculations

The objective of this study is to pilot test the newly adapted Intimacy Enhancement study and to allow us to calculate effect sizes that will inform a larger R01 trial that is expected to follow from this study. We selected 30 couples to participate in this trial because it is a large enough sample to provide ample pilot data while maintaining adequate feasibility in the time allotted. Further, we have chosen a 2:1 allocation to the Intimacy Enhancement condition, which allows us to gather greater information from participants in this condition, our primary interest, relative to the Couple Education condition.

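### The completer effect size takes no account of the age stratum used in randomisation, so age imbalance from drop-out goes unadjusted in the main calculation (a minor point)

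*Combined protocol and SAP*

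**What the plan says.** Section 4.5.1 sets the design: "Couples will be randomized with an allocation ratio of 2:1 to either the IE or the Educational Control (Living Healthy Together) condition", and this is done "with stratification by age at diagnosis (≤ 45 vs. > 45) using the age obtained by patients during the screening".

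Section 13.1.2.3 defines the effect size for every efficacy outcome. The numerator is formed by "subtracting the mean control group change score from the mean IE group change score". For the denominator, "This difference is then divided by the standard deviation of the pooled change score". No stratum term, covariate, standard error, confidence interval or test is planned.

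The calculation is run on completers, on the ground that "our primary goal through the analyses for this aim is to generate effect sizes for a larger planned study". An intent-to-treat version is also foreseen. Sections 10.0 and 13.1.2.3 provide for seeking post-treatment data from couples who drop out, and patients with none have their baseline values used. That last rule does not mention partners.

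Efficacy is not the primary outcome; section 13.1.1.2 states: "Secondary outcomes are preliminary efficacy of the study in patient and partner sexual outcomes". The sample size is pragmatic (section 13.2.4): "We selected 30 couples to participate in this trial because it is a large enough sample to provide ample pilot data".

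**The concern.** The design treats age group as worth balancing, but the analysis neither uses it nor checks it in the set on which the main effect sizes are computed. The protection from stratification can be lost between randomisation and the completer set.

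Drop-out is realistic on the plan's own evidence. The two earlier pilots in section 3.2 retained 9 of 14 and 18 of 23 couples, losses of 5/14 = 36% and 5/23 = 22%. Section 4.5.1 itself worries about drop-out that differs by arm: it keeps the allocation from couples until Session 1, and that protection ends there.

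The effect sizes are meant to inform a larger trial, whose sample size scales with 1/d². If the true effect were 0.5 (assumed), an error of 0.12 either way would multiply the required size by (0.5/0.62)² = 0.65 or (0.5/0.38)² = 1.73.

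**Working it through.** **Inputs from the documents.** 30 couples, 2:1, so about 20 vs 10; two age strata; raw difference in mean change; completers as the main set. The 30% attrition benchmark in section 13.1.2.1 serves as the drop-out scenario and leaves about 14 vs 7.

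**Assumed, because the documents give no figure.** Share aged ≤ 45 of 20%, 30% or 50%; difference in mean change between strata (g) of 0 to 0.8 within-stratum SD; 2:1 held exactly within each stratum. Section 4.5.1 does not describe the blocking.

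The plan gives no power, SD or target effect, so there is no stated figure to reproduce.

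**1. Sampling error of the raw effect size.** SE = sqrt((n1+n2)/(n1·n2) + d²/(2(n1+n2))).
- 20 vs 10: sqrt(30/200) = 0.387 at d = 0; sqrt(0.150 + 0.64/60) = 0.401 at d = 0.8.
- 14 vs 7: sqrt(21/98) = 0.463 at d = 0; sqrt(0.214 + 0.64/42) = 0.479 at d = 0.8.

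**2. No drop-out.** With 2:1 held within strata, both arms have the same share aged ≤ 45, so the raw and stratum-adjusted differences coincide. In simulation (4,000 runs per scenario, true effect 0) their sampling SDs were equal, at 0.38-0.40.

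**3. Random 30% drop-out.** The 95th percentile of the absolute difference between arms in share aged ≤ 45 was 0.22-0.29. Average bias was nil. Sampling SD was 0.472-0.491 raw and 0.466-0.486 adjusted. Adjustment made it worse by up to 0.006 when age had no effect and better by up to 0.006 when g = 0.8.

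**4. Drop-out related to age and arm.** Suppose 60% of younger IE couples and 30% of all others are lost. With initial share p, the expected share aged ≤ 45 among IE completers is 0.4p/(0.4p + 0.7(1−p)); among controls it stays p.
- p = 0.2: 0.08/0.64 = 0.125, a gap of 0.075
- p = 0.3: 0.12/0.61 = 0.197, a gap of 0.103
- p = 0.5: 0.20/0.55 = 0.364, a gap of 0.136

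Bias of the raw difference is approximately gap × g. By hand, with the simulated value in brackets (absolute values):

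| g | p = 0.2 | p = 0.3 | p = 0.5 |
|---|---|---|---|
| 0.3 | 0.023 (0.017) | 0.031 (0.030) | 0.041 (0.053) |
| 0.5 | 0.038 (0.041) | 0.052 (0.051) | 0.068 (0.068) |
| 0.8 | 0.060 (0.064) | 0.083 (0.081) | 0.109 (0.119) |

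The stratum-adjusted estimate was within 0.007 of zero throughout. Simulation error on each mean is about 0.48/sqrt(4000) = 0.008. The sign depends on which age group changes more and which drops out. The unit is the within-stratum SD; on the total SD the largest value is slightly smaller, 0.119/sqrt(1 + 0.8²·0.5·0.5) = 0.110.

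**5. Price of adjusting when age does not matter (g = 0).** Under the selective drop-out of step 4, sampling SD rose from 0.477-0.493 to 0.491-0.509, by at most 0.016.

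**The case against.** The strongest defence is proportionality. This is a 30-couple pilot with efficacy secondary and descriptive, and stratifying for balance and then reporting a simple effect size is a defensible choice. The bias needs two things the documents do not establish: that age predicts change (a fixed age difference in level cancels in a change score) and that drop-out differs by age and arm. Even the largest simulated bias is about a quarter of the sampling error. All of this stands, and it makes the point minor.

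The intent-to-treat version is a partial answer. It keeps randomised patients in and so restores their age balance. Where no post-treatment survey is obtained, however, it does so by assuming zero change, and it gives no rule for partners, whose outcomes are also efficacy outcomes.

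Two stronger readings are tempting and are not supported:

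- *A reader might infer that ignoring the strata wastes precision.* An assumed R² of 5-15% would suggest 30/(1−R²) = 31.6 to 35.3, a loss of 1.6 to 5.3 couples. That formula treats the design as unstratified. With balanced strata the two estimates are the same, and adjustment could only shrink a reported standard error, which this plan does not include.
- *A reader might infer that losing one or two couples is enough to matter.* Start both arms at 50% aged ≤ 45 and take g = 0.5. Losing one young control couple shifts the raw estimate by (5/10 − 4/9) × 0.5 = 0.028 SD; losing two, by (5/10 − 3/8) × 0.5 = 0.063 SD. A shift of (7/14 − 2/7) × 0.5 = 0.107 SD takes nine lost couples, with all three lost controls aged ≤ 45.

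**Conclusion.** The gap is real but minor. The main effect-size calculation neither adjusts for nor checks the randomisation stratum, and the completer set is where stratified balance can be lost. The plausible bias is about 0.02-0.12 SD, conditional on an assumed 0.3-0.8 SD difference in change between age strata and on drop-out that depends on both age and arm. Against a standard error of about 0.46-0.48, it would not dominate any single estimate. Unlike sampling error, it would not show in a confidence interval, and it is nearly free to remove. Under random drop-out there is only chance imbalance, without average bias. The documents do not support a claim of lost precision.

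**What to change.** In section 13.1.2.3, keep the raw effect size and add:

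1. the IE-minus-LHT difference in mean change from a linear model with arm and the age stratum used at randomisation, for patient and partner outcomes alike;
2. division of that difference by the same SD of the pooled change score as the raw effect size;
3. the share aged ≤ 45 by arm among completers, shown beside both estimates.

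The model's residual SD should not be the divisor. It would raise the effect size by 1/sqrt(1−R²), which is 1.026 at an assumed R² of 5% and 1.085 at 15%. The estimate would then no longer be comparable with the raw one, and the larger trial could be undersized if planned on the raw scale.

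No new data are needed, since the stratum is recorded for randomisation. The cost is a few lines of text, one degree of freedom and the small extra variability shown in the working if age does not predict change. If one age stratum has no completers, the model cannot be fitted and the raw figure stands alone; the plan should say so.

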10.0 Off-Study Criteria

Any participant may leave the study at any time due to distress or other reasons. We do not have a priori reasons for letting participants off the study. An exception would be if a patient or partner experiences significant psychological or marital distress during the study such that it is deemed detrimental for them to continue in our study at the expense of receiving psychological or mental health services. If this happens, we will follow the procedures listed below for Adverse Event reporting, and will recommend that the couple not continue in this study but rather receive appropriate referrals, as described below in section 15.0. We will track such events, as described below, and we expect them to be extremely rare.

In the case of attrition after randomization to either intervention, the participant and his or her partner may be asked if they would be willing to remain in the study for data collection in four weeks which will enable us to conduct intent-to-treat analyses (or the length of time that would coincide with the end of their treatment sessions).

If a patient's disease recurs or needs to start active treatment during the study, they will be allowed to remain on the study, if they choose, and this information will be tracked in their research files pertaining to their medical records. Because the duration of the study involvement is relatively brief, we expect these circumstances to be infrequent.

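### Effect sizes for the R01 come from a loosely defined completer subset, and the added intent-to-treat analysis imputes zero change for patients and has no rule for partners

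*Combined protocol and SAP*

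**What the plan says.** Section 13.1.2.3 defines the effect size as the difference between arms in mean pre-post change, divided by the pooled standard deviation of change. It then chooses the analysis set. Because "our primary goal through the analyses for this aim is to generate effect sizes for a larger planned study", the plan says "we will conduct the analyses described above using data from study completers". Section 13.2.4 confirms that these effect sizes are to inform the R01.

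The next sentence adds a second analysis: "However, we will also attempt to obtain post-treatment surveys even for couples who have dropped out of the study during the intervention phase", so that intent-to-treat analyses can be done. Its missing-data rule is: "Patients without any post-treatment data will have baseline data used in these analyses". Partner sexual and relationship outcomes are analysed too (sections 13.1.1.2 and 13.1.2.3), but this rule names patients only.

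No section formally defines a completer. Section 13.1.2.1 says "80% of participants completing the 4 sessions is considered adequate", but that is a feasibility criterion and does not define an analysis set. Section 4.6 describes completing the study as running from consent to the post-treatment assessment.

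On contact after stopping, section 10.0 says that a participant and partner who leave after randomisation "may be asked if they would be willing to remain in the study for data collection in four weeks". Section 13.1.2.3 is firmer about seeking those surveys.

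**The concern.** A completer set is selected on what happens after allocation. If staying in is related to outcome, and differently so in the two arms, the completer effect size no longer estimates the effect in the couples who were randomised. Planning a larger trial is no reason to accept that restriction, and the plan already intends to collect surveys from couples who stop. On the natural reading, which the text does not state outright, those surveys feed only the intent-to-treat analysis and not the planning figure.

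The intent-to-treat analysis does not settle the matter. A baseline score used as the post-treatment score makes the change exactly zero. That is often taken to be conservative, but if both arms improve and missingness differs by arm, it can push the estimate either way. For partners, two analysts could apply different rules to the same data.

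At stake is the usefulness of a planning figure. The primary outcomes, feasibility and acceptability, are not affected.

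**Working it through.** **No planned figure to reproduce.** The 30 couples are justified by feasibility, with no alpha, power, effect size or SD (section 13.2.4). Allocation of 2:1 gives 20 and 10.

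**Inputs from the documents**
- Non-completion of 20%, the complement of the 80% session target, and 30%, the plan's example attrition limit (both section 13.1.2.1).
- Earlier colorectal pilots (section 3.2): 9 of 14 and 18 of 23 couples completed, so 5/14 = 36% and 5/23 = 22% did not.

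**Assumptions, because the documents give no values for this trial**
- Change SD of 1 in each arm, pooled within arm.
- A completer d of 0.50 in steps 1 and 2.
- True mean changes of 0.8 (IE) and 0.3 (control) in step 3.
- The split of missing couples between arms.

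**Step 1: completers against all randomised couples.** Let a be the dropout share in each arm. Results are in completer SD units.
- Dropout unrelated to outcome: d stays at 0.50.
- IE dropouts gain nothing over control: 0.5(1 − a) = 0.40 at a = 0.20 and 0.35 at a = 0.30.
- Only control dropouts do worse, by 0.5 SD: 0.5 + 0.5a = 0.60 and 0.65.

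The completer figure may therefore be too high, too low or correct.

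**Step 2: what retrieved surveys recover.** In the case where IE dropouts gain nothing, if a share r of dropouts returns a survey and is included, the estimate is 0.5(1 − a)/(1 − a + ar). With r = 0.5:
- a = 0.20: 0.40/0.90 = 0.44, against 0.40 for all randomised.
- a = 0.30: 0.35/0.85 = 0.41, against 0.35.

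Including them removes part of the bias but not all of it.

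**Step 3: the zero-change rule, with missingness unrelated to outcome.** If a share m of an arm with mean change μ is set to zero, the arm mean is (1 − m)μ and the arm variance is (1 − m) + m(1 − m)μ². Variances are pooled with weights 20 and 10. The true d is 0.50.

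| Missing IE / control | Difference in means | Pooled SD | d |
|---|---|---|---|
| 20% / 20% | 0.64 − 0.24 = 0.40 | 0.934 | 0.43 |
| 6 of 20 / 1 of 10 | 0.56 − 0.27 = 0.29 | 0.927 | 0.31 |
| 2 of 20 / 3 of 10 | 0.72 − 0.21 = 0.51 | 0.937 | 0.54 |

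The last two rows correspond to overall missingness of 7/30 = 23% and 5/30 = 17%, both inside the 30% limit. In these cases an analysis of the surveys actually returned would be centred on 0.50.

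**Step 4: sampling error.** SE(d) = √[(n₁ + n₂)/(n₁n₂) + d²/(2(n₁ + n₂))] at d = 0.50:
- 20 and 10: √(0.1500 + 0.0042) = 0.39, giving a 95% CI of 0.50 ± 1.96 × 0.393, or −0.27 to 1.27.
- 16 and 8: 0.44.
- 14 and 7: 0.47.

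The largest shift above is 0.50 − 0.31 = 0.19, and 0.19/0.393 is about half a standard error.

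**The case against.** The case on the other side is substantial. Efficacy is a secondary, descriptive outcome of a 30-couple pilot. The completer choice is disclosed with a reason. Retrieval of surveys, an intent-to-treat analysis and a missing-data rule for patients are already planned. Sampling error exceeds every shift computed. The proposed lead estimate is itself based on returned surveys, so it is also conditioned on something after randomisation. If completer simply means survey returned, it is the same calculation. All of this stands, and it is why the point is minor. It does not explain why the planning figure should leave out surveys that the study intends to obtain, or what happens to missing partner data.

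Several stronger readings are tempting, and the documents do not support them.
- *The completer effect size will be inflated.* Nothing shows that dropout will be related to outcome or will differ by arm. For distress-related discontinuations section 10.0 says "we expect them to be extremely rare". Assignment is concealed "to reduce the chances for unequal drop-out prior to Session 1". The control is matched for time and attention (section 4.5.3), and credibility is compared between arms (section 16.1.1).
- *The earlier pilots predict 22% to 36% loss from the randomised comparison.* Section 3.2 does not say when those couples were lost, the first pilot had no control arm, and both were in colorectal cancer. Here randomisation follows consent, baseline surveys and scheduling of the first session (section 4.5.1), so earlier losses never enter the comparison.
- *The completer set is wholly undefined.* Section 4.6, and the contrast with couples who dropped out, suggest couples who reach the post-treatment assessment. What stays unclear is narrower: couples who stop sessions but return a survey, and couples in which only one member returns it.

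**Conclusion.** The point holds as a minor, cheap improvement. The planning effect sizes rest on a post-randomisation subset that is only partly described. The additional intent-to-treat analysis uses a zero-change rule that can understate or overstate the effect when missingness differs by arm, and it has no stated rule for partners.

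The size and direction of any bias are unknown. Every effect size and arm split used here is assumed. Under those assumptions an effect of 0.50 becomes 0.31 or 0.54 under the zero-change rule, and a completer d of 0.50 may correspond to anything from 0.35 to 0.65 in all randomised couples. These shifts are within sampling error. They do not show that the R01 would be wrongly sized, and they do not touch the feasibility and acceptability outcomes.

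**What to change.** In section 13.1.2.3:
- Make the lead effect size, and the one used for R01 planning, the existing change-score d by assigned arm. Use every post-treatment survey obtained, including those from couples who stopped sessions, and report patients and partners separately.
- Give a confidence interval for each d and the amount of missing data by arm.
- State that surveys not returned are assumed missing at random within arm, and that the estimate is therefore not fully protected by randomisation.
- Keep two labelled sensitivity analyses: completers, with the term defined (sessions, survey, one or both members), and baseline carried forward, applied to patients and partners alike.

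Separately, sections 10.0 and 13.1.2.3 differ on whether couples who stop may be asked, or will be approached, for the post-treatment survey. The sponsor should reconcile them. That concerns participant contact and so is more than a change of SAP wording.

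The analysis changes cost only wording, since retrieval and an intent-to-treat analysis are already planned. The downside is that the planning effect size may look less favourable. Bias from outcome-related non-return would remain.
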